### 9.10. EPWORTH SLEEPINESS SCALE

The Epworth Sleepiness Scale is used to determine the level of daytime sleepiness. There are 8 situations listed for which patients rate their likelihood of dozing or sleeping (0=would never doze or sleep, 1=slight chance of dozing or sleeping, 2=moderate chance of dozing or sleeping, and 3=high chance of dozing or sleeping). The total score is the sum of 8 item scores and can range between 0 and 24. In case of missing item scores, the missing value will be replaced by the average of non-missing scores at the same visit from the same patient. In case all item scores are missing, the total score will be set as missing. The higher total score indicates the higher level of daytime sleepiness. A score of 10 or more is considered sleepy, and a score of 18 or more is very sleepy.

All Epworth Sleepiness Scale data will be listed. The total score and change from baseline to each visit will be summarized by treatment group and overall (for handling of data from the ET visit, see Section 6.4). The total score and change from baseline (TV1) and Last Day of Treatment to days 1, 3, 6, 8, 11, 14, 17, 24, and 28 after Last Day of Treatment will also be summarized. LDOT is defined as assessment taken on TV6 or ET for patients who didn't enrolled into the sub-study and TV4, TV5 or TV6 for patients who enrolled into sub-study.

### 9.11. QUESTIONNAIRE FOR IMPULSIVE-COMPULSIVE DISORDERS IN PARKINSON'S DISEASE

The QUIP is an instrument used to measure the extent of impulsive and compulsive behaviors in PD patients. The QUIP has 3 sections: Section 1 assesses any impulsive control disorder (gambling, sexual, buying, and eating disorders); Section 2 assesses other compulsive behaviors (punding, hobbyism, and walkabout); and Section 3 assesses compulsive medication use.

## Statistical Analysis Plan

The frequency and percentage of patients with positive response for each of the item within each section will be summarized by treatment group and overall. The assessment of positive response for each item will be based on the table below.

Section and Item	Number of items with positive response
A. Impulse Control Disorders	
Compulsive gambling	any 2 of the 5 gambling items
Compulsive sexual behavior	any 1 of the 5 sexual behavior items
Compulsive buying	any 1 of the 5 buying items
Compulsive eating	any 2 of the 5 eating items
B. Other Compulsive Behaviors	
Hobbyism	item #1A
Punding	item #1B
Walkabout	item #1C
C. Compulsive Medication Use	items #1 and #4

### 9.12. UPDRS PART 4

Changes from TV1 (pre-dose) to each visit (pre-dose) in UPDRS Part 4 sum scores and each sub-scores (Dyskinesias and Fluctuations) will be summarized and analyzed using similar MMRM methods as for the spirometry data.

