- ECG: HR, PR, QRS, QT and RR intervals, QTcB (Bazett’s correction formula calculated as $QT/RR^{1/2}$) and QTcF (Fridericia’s correction formula calculated as $QT/RR^{1/3}$). ECG parameter values or parameter changes of potential clinical concern will be tabulated.
- Spirometry: FEV1, FVC, and the FEV1/FVC ratio during specified treatment visits and over the course of the study will be evaluated. The number and proportion of patients with pre-specified changes in spirometry parameters will be tabulated.
- Changes from baseline to follow-up in the rating scales for assessing suicidality, somnolence, and impulse control disorders will be summarized descriptively.
- For the AWQ, DDS-PC, PHQ-9, Epworth Sleepiness Scale, C-SSRS, and UPDRS Parts 1 and 2, the change from baseline to days 1, 3, 6, 8, 11, 14, 17, 24, and 28 of the withdrawal symptom assessment period will be summarized descriptively.

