## Statistical Analysis Plan

### 2. PURPOSE

The purpose of this statistical analysis plan (SAP) is to ensure that the data listings, summary tables and figures which will be produced, and the statistical methodologies that will be used, are complete and appropriate to allow valid conclusions regarding the study objectives.

This SAP describes the statistical analysis as it is foreseen at the time of planning the study. The SAP will serve as a compliment to the study protocol and supersedes it in case of differences. In case of major differences between the study protocol and SAP (e.g. changes in the analysis related to the primary endpoint) protocol amendment will be considered. The SAP may be updated during the conduct of the study and will be finalized before the data base lock. However, the analyses defined after the blind of study CVT-301-004 has been broken will be considered as exploratory.

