## Statistical Analysis Plan

- If the start day is missing, the first day of the month will be used.
- If the start day and month are missing, then the first day of the first month (January) will be used.

The original date and time will be shown on all listings of AEs. Listings will be provided for all AEs, serious AEs, AEs leading to study drug discontinuation, AEs leading to dose reduction, and deaths.

TEAEs will be summarized by SOC and PT for each treatment group and CVT-301 overall. TEAEs with onset after the treatment period are attributed to the treatment group during the treatment period. Both event and patient counts, where applicable, will be summarized. The counts will be complemented by percentages will be calculated for the patient counts unless otherwise specified. In addition, the incidence of TEAEs, normalized for duration of exposure to CVT-301 will be presented (number of TEAEs divided by the total exposure to CVT-301, measured as patient years).

- An overall summary of the number and percentage of patients reporting TEAEs and the number of TEAE events, drug-related TEAEs, severe TEAEs, serious TEAEs, TEAEs leading to dose interruption, TEAEs leading to study drug discontinuation, TEAEs leading to dose reduction and TEAEs leading to death
- TEAEs by SOC and PT, both as event and patient counts
- TEAEs by PT, both as event and patient counts
- Drug-related TEAEs by SOC and PT, both as event and patient counts
- Severe TEAEs by SOC and PT, both as event and patient counts
- Drug-related TEAEs by SOC, PT and severity, as event counts; percentages will be calculated for the event count out of total number of events
- Drug-related TEAEs by SOC, PT and relationship, as event counts; percentages will be calculated for the event count out of total number of events
- Serious TEAEs by SOC and PT, both as event and patient counts
- TEAEs leading to study drug interruption, both as event and patient counts
- TEAEs leading to study drug withdrawal, both as event and patient counts
- TEAEs leading to dose reduction, both as event and patient counts
- Most common AEs, both as event and patient counts, most common TEAEs is defined any AE preferred term occurred in greater than 10% total patients
- Time to first onset of most common AEs, classified as 0-1 months, >1-3 months, >3-6 months, >6-9 months and after 9 months, where the date of TEAE onset will be used as the time point for classification

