## Statistical Analysis Plan

### 11. CHANGE FROM ANALYSIS PLANNED IN PROTOCOL

The protocol stated that the data for patients who were enrolled in the CVT-301-004 study, the CVT-301-009 study and for the CVT-301-naïve patients study will be primarily analyzed together, while the patients who were enrolled in the CVT-301-003 study will be analyzed separately. In the SAP, the patients enrolled from CVT-301-003 and CVT-301-009 will not be included in efficacy summaries (i.e. the patients enrolled from CVT-301-003 and CVT-301-009 will be excluded from ITT population) due to the different study designs. Instead the efficacy data from patients who were enrolled in the CVT-301-003 or CVT-301-009 study will be analyzed separately, as data listings. The rationale for excluding the CVT-301-003 patients from the efficacy summaries is the gap between the end of CVT-301-003 and start of CVT-301-004E.

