## Statistical Analysis Plan

Table 14.3.4.5.11.2	Summary of Spirometry(Neurology Office):Categories of Change from Baseline for FEV1 and FVC by Treatment/Study and Visit (Safety Population)
Table 14.3.4.5.11.3	Summary of Spirometry(Neurology Office):Categories of Change from Baseline for FEV1 by Treatment Group, Visit and Smoker Status (Safety Population)
Table 14.3.4.5.11.4	Summary of Spirometry(Neurology Office):Categories of Change from Baseline for FEV1 by Treatment/Study, Visit and Smoker Status(Safety Population)
Table 14.3.4.5.12.1	Summary of Spirometry(Neurology Office):Categories of Change from Baseline for FEV1/FVC by Treatment Group and Visit (Safety Population)
Table 14.3.4.5.12.2	Summary of Spirometry(Neurology Office):Categories of Change from Baseline for FEV1/FVC by Treatment/Study and Visit (Safety Population)
Table 14.3.4.5.13.1	Summary of Spirometry (Neurology Office): Actual Values and Change from Pre-dose for FEV1 and FVC at TV1 (Safety Population)
Table 14.3.4.5.13.2	Summary of Spirometry (Neurology Office): Actual Values and Change from Pre-dose for FEV1/FVC at TV1 (Safety Population)
Table 14.3.4.5.13.3	Summary of Spirometry (Neurology Office): Actual Values and Change from Pre-dose for FEV1 at TV1 by Smoker Status (Safety Population)
Table 14.3.4.5.14.1	Summary of Spirometry (Neurology Office): Categories of Percent Change from Pre-dose for FEV1, FVC at TV1 (Safety Population)
Table 14.3.4.5.14.2	Summary of Spirometry (Neurology Office): Categories of Percent Change from Pre-dose for FEV1/FVC at TV1 (Safety Population)
Table 14.3.4.5.14.3	Summary of Spirometry (Neurology Office): Categories of Percent Change from Pre-dose for FEV1 at TV1 by Smoker Status (Safety Population)
Table 14.3.4.6.1	Summary of Columbia-Suicide Severity Rating Scale (C-SSRS) by Treatment Group and Visit (Safety Population)
Table 14.3.4.6.2	Shift from Baseline in Columbia-Suicide Severity Rating Scale (C-SSRS) by Treatment Group and Visit (Safety Population)
Table 14.3.4.6.3	Summary of Self-Reported Columbia-Suicide Severity Rating Scale (C-SSRS) by Treatment Group and Visit (Safety Population)
Table 14.3.4.7	Summary of Epworth Sleepiness Scale Total Score: Actual Values and Change from Baseline by Treatment Group and Visit (Safety Population)

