Table 14.3.4.7.1	Summary of Epworth Sleepiness Scale Total Score: Change from Baseline (TV1) and Last Day of Treatment (LDOT) to Days 1, 3, 6, 8, 11, 14, 17, 24, and 28 after LDOT by Treatment Group (Safety Population)
Table 14.3.4.8	Summary of Questionnaire for Impulsive-Compulsive Disorders in Parkinson's (QUIP) by Treatment Group and Visit (Safety Population)
Table 14.3.4.9.1	MMRM Analysis of UPDRS Part 4: Change from Baseline in the UPDRS Part 4 Score by Treatment Group and Visit (Safety Population)
Table 14.3.4.9.2	MMRM Analysis of UPDRS Part 4 Dyskinesias Score: Change from Baseline in the UPDRS Part 4 Score by Treatment Group and Visit (Safety Population)

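### The SAP does not carry over the protocol's change-from-baseline summary for QUIP, and does not declare the difference

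*SAP*

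**What the plan says.** Protocol 12.5 states, in its running text and again in its list of variables: "Changes from baseline to follow-up in the rating scales for assessing suicidality, somnolence, and impulse control disorders will be summarized descriptively". The synopsis says the same.

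For QUIP, the protocol's impulse-control scale, SAP 9.11 sets thresholds for a positive response in eight item groups (four impulse control disorders, three other compulsive behaviors, and compulsive medication use). It then plans: "The frequency and percentage of patients with positive response for each of the item within each section will be summarized by treatment group", with a pooled total as well. The table index (SAP 14) has a single QUIP entry, Table 14.3.4.8: "Summary of Questionnaire for Impulsive-Compulsive Disorders in Parkinson's (QUIP) by Treatment Group and Visit (Safety Population". Individual data go to Listing 16.2.8.2.7.

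On precedence, SAP 2 says: "The SAP will serve as a compliment to the study protocol and supersedes it in case of differences". SAP 11, which records changes from the protocol, covers only efficacy data from two feeder studies: "the patients enrolled from CVT-301-003 and CVT-301-009 will not be included in efficacy summaries".

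**The concern.** The protocol promises the same kind of summary for three scales and the SAP specifies it for two. Because the SAP governs where the documents differ, the QUIP commitment lapses without a stated reason.

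The question a reader brings to QUIP in a trial of inhaled levodopa is how many patients who were negative before CVT-301 became positive on it. QUIP is repeated at TV2 to TV6, so the data to answer this are collected. A percentage positive by group and visit does not answer it, because patients who become positive and patients who resolve offset each other.

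**Working it through.** There is no planned figure to reproduce, so this is mainly a comparison of texts.

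**1. The three scales in the protocol sentence**

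| Scale | SAP text | Table | Baseline comparison specified? |
|---|---|---|---|
| C-SSRS | 9.9 | 14.3.4.6.2 | Yes: "Shift from Baseline in Columbia-Suicide Severity Rating Scale (C-SSRS) by Treatment Group and Visit (Safety Population" |
| Epworth | 9.10 | 14.3.4.7 | Yes: "Summary of Epworth Sleepiness Scale Total Score: Actual Values and Change from Baseline by Treatment Group and Visit (Safety Population" |
| QUIP | 9.11 | 14.3.4.8 | Not stated in text or title |

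SAP 6.2 defines change from baseline as a subtraction. That is a formula; it creates no QUIP output.

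**2. What group percentages can identify**

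Take one item group and the same patients at baseline and follow-up. Let b and f be the proportions positive at the two times. Let n be the proportion newly positive and r the proportion resolved, both as shares of all patients. Then:

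- f − b = n − r, so the two percentages fix only the difference between n and r.
- n can lie anywhere from max(0, f − b) to min(f, 1 − b).
- If the percentage is unchanged (f = b = p), n can lie anywhere from 0 to min(p, 1 − p).

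The documents give no QUIP rates. For assumed values of p of 5%, 10% and 20%, an unchanged percentage is compatible with new positives in 0–5%, 0–10% and 0–20% of patients. These are logical limits, not expectations.

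**3. Where a newly positive patient would appear**

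- In Table 14.3.4.8, counted as positive but not separated from persisting positives.
- In the adverse event tables, if the site reports an event. Protocol 11.1.8 asks for new symptoms and syndromes, and SAP 9.4 plans "TEAEs by SOC and PT, both as event and patient counts". Protocol 11.1.12.4 (QUIP) has no rule that a positive screen be recorded as an AE; Protocol 11.1.1 does have such a rule for noteworthy changes at physical examination.
- Otherwise, as a new positive, only by reading Listing 16.2.8.2.7.

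The DDS-PC does not fill the gap. It is a separate instrument, given at TV1 and around the withdrawal assessment period (Protocol 11.1.12.5).

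**4. Which baseline a shift table would use**

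The rules disagree for patients who received placebo in CVT-301-004:

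- Protocol 11.1.12.4: TV1 of CVT-301-004, for all CVT-301-004 patients.
- Protocol 12.3: TV1 of 004E for placebo patients. No QUIP is scheduled there for CVT-301-004 patients (Protocol 10.1.3.2 and Appendix 4).
- SAP 6.2: last non-missing value before the first CVT-301 dose in 004E.

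Under SAP 6.2 the value must therefore come from CVT-301-004. Whether it is that study's TV1 or a later visit depends on a schedule not contained in these documents.

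**The case against.** The best counter-argument is that the protocol requires only a descriptive summary of change, not a within-patient shift table. For a positive/negative measure, percentages by visit with baseline among the visits are an ordinary way to show change. Table 14.3.4.8 is by visit and the shells are not available, so a reader who concludes that the SAP omits baseline altogether goes further than the text allows. That stands. It does not remove the gap, because a baseline column still gives only f − b. Nor does it explain why C-SSRS and Epworth have explicit baseline wording and QUIP does not.

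A second tempting inference is that new positives go uncounted. They do not: they are in Table 14.3.4.8, and in the TEAE tables when reported as events. What is missing is their identification as new.

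Third, the consequence is small. The summary is secondary and descriptive, there is no untreated arm, no decision rule depends on it, and individual data are listed. That also stands, and it sets the weight of the point.

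Finally, the remedy is not quite free. The baseline for placebo rollovers needs a decision, and an early parent-study value would attribute to CVT-301 any conversions that occurred on placebo. This is a fair criticism of a loosely specified shift table, and the fix has to address it.

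**Conclusion.** The difference between protocol and SAP is real and undeclared. The SAP commits only to frequency and percentage positive for QUIP, while the other two scales named alongside it get a shift or change-from-baseline summary. The practical loss is limited: the number of baseline-negative patients who become positive appears in no specified table and has to be taken from a listing.

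The conclusion rests on the SAP text and table titles and assumes that the unseen shell for Table 14.3.4.8 contains no shift or new-onset rows. No size can be attached, because the documents contain no QUIP rates; the limits above show only that an unchanged percentage does not rule out new onset. This is a minor improvement to a descriptive safety summary. Nothing in the documents supports reading it as a threat to the primary spirometry analysis or as a failure to collect or list the data.

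**What to change.** In SAP 9.11, for each QUIP item group, add a descriptive shift table of baseline (negative/positive) by each post-baseline visit (negative/positive/missing), by treatment group and overall. Show the number and percentage newly positive among baseline-negative patients assessed at that visit. Keep Table 14.3.4.8.

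State the baseline explicitly, following SAP 6.2:

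- Patients treated with CVT-301 in CVT-301-004: last QUIP before the first CVT-301 dose in that study.
- CVT-301-004 placebo rollovers: last non-missing QUIP before the first CVT-301 dose in 004E, taken from CVT-301-004. Add a footnote that, if this is the CVT-301-004 TV1 value, conversions during placebo treatment cannot be separated from onset on CVT-301.
- All other patients: last non-missing QUIP before the first CVT-301 dose in 004E.

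If the sponsor prefers to keep percentages only, SAP 11 should declare and justify the departure from Protocol 12.5.

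The cost is a paragraph of SAP text, one extra table, and merging parent-study QUIP baselines for the rollovers. No visit, assessment or primary analysis changes.

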### 9.13. EXAMINER-RATED DYSKINESIA

The occurrence and severity will be tabulated by treatment group and visit. The observed cases will be used in the summaries. No formal statistical methods will be used.

### 9.14. AMPHETAMINE WITHDRAWAL QUESTIONNAIRE (AWQ)

The actual values and changes from baseline (TV1) and LDOT to days 1, 3, 6, 8, 11, 14, 17, 24, and 28 after LDOT in AWQ total score will be summarized descriptively for patients in safety population. LDOT is defined as assessment taken on TV6 or ET for patients who didn't enrolled into the sub-study and TV4, TV5 or TV6 for patients who enrolled into sub-study.

### 9.15. DOPAMINE DYSREGULATION SYNDROME - PATIENT AND CAREGIVER INVENTORY (DDS-PC)

The actual values and changes from baseline (TV1) and Last Day of Treatment to days 1, 3, 6, 8, 11, 14, 17, 24, and 28 after Last Day of Treatment in DDS-PC total score will be summarized descriptively for patients in safety population. LDOT is defined as

1003804

Civitas Therapeutics, Inc.

CVT-301-004E

SAP Version 2.0

## Statistical Analysis Plan

assessment taken on TV6 or ET for patients who didn't enrolled into the sub-study and TV4, TV5 or TV6 for patients who enrolled into sub-study.

### **9.16. MOVEMENT DISORDER SOCIETY - UNIFIED PARKINSON'S DISEASE RATING SCALE (MDS-UPDRS)**

The MDS-UPDRS Part 1 and Part 2 value will be summarized descriptively on days 1, 3, 6, 8, 11, 14, 17, 24, and 28 after Last Day of Treatment by treatment for patients in the safety population.

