- Complete the C-SSRS and Epworth Sleepiness Scale, (preferably in the ON state).
- Complete the UPDRS Parts 1 and 2 (preferably in the ON state).
- Patient will complete the Impact of Parkinson's OFF Episodes Patient Survey (preferably in an ON state)
- Re-train patients on the proper use of the inhaler with sham capsules, including a review of the IFU.
- Distribute the PD Diary and review instructions for recording time asleep, time OFF, time ON without dyskinesia, time ON with non-troublesome dyskinesia, and time ON with troublesome dyskinesia (to be completed for the 3 consecutive days prior to TV2, TV3, TV4, TV5, and TV6).
- Distribute the Inhaled Dosing Log and review instructions for recording the number of times the inhaler was used and the number of capsules used for each inhalation treatment (to be completed daily throughout the 13-month treatment period).
- Distribute study drug kits to patients.

Study Drug Dosing

Immediately pre-dose, perform a spirometry assessment (record the patient's ON/OFF state on the spirometry source record). Under clinic staff supervision, preferably between 2 and 5 hours after receiving their standard dose of PD medication (in the OFF state), patients will prepare and self-administer their first dose of blinded study drug from the study drug kits that were provided (i.e., 2 capsule inhalations of either CVT-301 DL1 or CVT-301 DL2). Patients will be permitted sips of water between capsule inhalations as needed.

Note: Instructions for how to properly use the CVT-301 system are outlined in the Instructions for Use document that is included with every CVT-301 study kit. Refer to [Appendix 17](#) for additional system information.

Post-dose (10 – 60 minutes)

After dosing, patients will undergo serial safety evaluations. Refer to [Appendix 4](#) for the detailed time and events table. The following post-dose safety evaluations will be performed:

- Record vital signs (standard and orthostatic BP and HR) at 20 and 60 minutes. Post-dose.
- Record RR at 10, 20, 30, and 60 minutes post-dose.

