10.1.4. Sub-Study to Assess Potential Withdrawal Symptoms

After patients are consented to protocol Version 5.2, they will participate in a withdrawal symptom sub-study at the end of TV4, TV5, or TV6, depending on which of the visits is the next scheduled one for the patient. In addition to the assessments detailed in the previous sections for the treatment visit, the AWQ and DDS-PC will be performed upon arrival in the ON state, and the UPDRS Part 1 will be performed preferably in the ON state.

When study activities for the visit are completed, patients will begin a 28-day period of assessment of potential drug withdrawal symptoms. To this end, patients who are at TV4 or TV5 at the time of consent will go on a study drug holiday for this time period. All patients in the withdrawal sub-study (patients consented to protocol Version 5.2) will be given copies of the AWQ, the DDS-PC, PHQ-9, Epworth Sleepiness Scale, C-SSRS (self-report version), and the self-administered MDS-UPDRS Parts 1B and 2 (Movement Disorder Society -UPDRS) to be completed at home at 1, 3, 6, 8, 11, 14, 17, 24, and 28 days after the treatment visit. Patients should fill out the questionnaires during their first ON state (after the intake of their first scheduled dose of standard oral PD medication) on each of these days. The site will call patients

at 14 (± 3) days after the treatment visit to remind them to complete the questionnaires, and to inquire about potential adverse events and changes in concomitant medications. Patients who enter the withdrawal sub-study after TV6 will also receive a call at 28 (± 3) days.

Patients who entered the study drug holiday will be scheduled to return to the clinic for a drug re-supply visit (see [Section 10.1.4.1](#)), and resumption of the full course of study treatment. Patients who entered the withdrawal sub-study after TV6 will be completed with the study after they return the questionnaires and undergo the DLco and spirometry assessment 4 to 5 weeks after completion of TV6, as described in [Section 10.1.3.9](#).

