11.2.7. Schwab & England Activities of Daily Living

The S&E ADL scale will be completed by a qualified rater upon arrival as indicated in the time and events tables in [Appendix 5](#) through [Appendix 10](#), preferably while the patient is in the ON state. The baseline assessment for CVT-301-naïve and [CVT-301-009](#) patients will be completed at TV1. The baseline assessment for [CVT-301-004](#) patients will have been completed at TV1 of [CVT-301-004](#) study.

11.2.8. UPDRS Part 2 and MDS-UPDRS Part 2

The UPDRS Part 2 is an evaluation of the ADL; this will be assessed by a qualified rater as indicated in the time and events tables in [Appendix 2](#) through [Appendix 10](#), preferably while the patient is in the ON state. The baseline assessment for CVT-301-naïve and [CVT-301-009](#) patients will be completed at TV1. The baseline assessment for [CVT-301-004](#) patients will have been completed at TV1 of [CVT-301-004](#) study (except for assessment of withdrawal symptoms). The self-administered MDS-UPDRS Part 2 will be completed at home during the withdrawal assessment period (see [Appendix 8](#) through [Appendix 10](#)).

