11.3.3. UPDRS Part 1 and MDS-UPDRS Part 1B

The UPDRS Part 1 assesses the non-motor impact of Parkinson's disease (PD) on patients' experiences of daily living, and will be performed at SV1 as part of the baseline characterization of the patient (not used to determine eligibility). Additionally, it will be performed at TV1 and at the visit at which the withdrawal assessment period begins (TV4, TV5, TV6 or Early Withdrawal). The self-administered MDS-UPDRS Part 1B will be completed at home during the withdrawal assessment period (see [Appendix 8](#) through [Appendix 10](#)).

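### UPDRS before withdrawal, MDS-UPDRS during it: the planned change over withdrawal Days 1 to 28 cannot be computed within either instrument

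*SAP*

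**What the plan says.** **The planned analysis.** Protocol 12.5, and the synopsis in nearly the same words, list several withdrawal scales for descriptive summary, ending with "UPDRS Parts 1 and 2, the change from baseline to days 1, 3, 6, 8, 11, 14, 17, 24, and 28" of the withdrawal period. The sentence names the UPDRS, without the MDS prefix.

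**What is collected on those days.** Protocol 11.3.3 says "The self-administered MDS-UPDRS Part 1B will be completed at home during the withdrawal assessment period". Protocol 11.2.8 says "The self-administered MDS-UPDRS Part 2 will be completed at home during the withdrawal assessment period". SAP 4.3 likewise places MDS-UPDRS Parts 1B and 2 in the withdrawal period only.

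**What is collected before withdrawal.** At TV1 both patient streams have the original UPDRS Parts 1 and 2 (Protocol 10.1.3.2 and 10.1.3.3). UPDRS Part 2 is also scheduled at each later treatment visit. At the visit that opens the withdrawal period, Protocol 10.1.4 adds Part 1: "the UPDRS Part 1 will be performed preferably in the ON state". Appendices 8 to 10 have the MDS-UPDRS forms handed out at that visit for later completion at home.

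**What the SAP analyses.** SAP 9.16 states "The MDS-UPDRS Part 1 and Part 2 value will be summarized descriptively" on the nine days. Tables 14.3.4.13.1 and 14.3.4.13.2 give actual values only. For AWQ and DDS-PC (SAP 9.14, 9.15), PHQ-9 (SAP 8.1) and Epworth (SAP 9.10), the SAP plans change from TV1 and from LDOT. Protocol 12.3 takes withdrawal assessments out of the general baseline rule and names no replacement.

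**The concern.** The sub-study exists to see whether symptoms worsen when study drug stops. For that, a scale needs a value on drug and a value off drug from the same instrument in the same patient. The MDS-UPDRS has only the second and the original UPDRS only the first.

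Nine off-drug means with no reference cannot separate worsening after stopping from a patient's usual level. They also mix change within patients with change in who returned a complete form, because one missing item sets the score to missing (SAP 4.3).

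MDS-UPDRS Parts 1B and 2 are named in the safety objectives (Protocol Section 6, SAP 3.3). Part 2 is the only activities-of-daily-living scale among the home forms. Patients are asked to fill in these forms nine times, and the plan omits the one completion that would make them interpretable.

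**Working it through.** No sample size, power or error-rate figure bears on this point. The check is a visit-by-visit trace of which instrument is scheduled when, using Protocol 10.1, 11.2.8, 11.3.3 and Appendices 4 to 10, with score definitions from SAP 4.2, 4.3 and 9.17.

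| Instrument | Items in the score | TV1 | Visit that opens withdrawal (TV4, TV5, TV6 or ET) | Withdrawal days |
|---|---|---|---|---|
| UPDRS Part 1 | 1 to 4 | yes | yes | none |
| UPDRS Part 2 | 5 to 17 | yes | yes | none |
| MDS-UPDRS Part 1B | 1.7 to 1.13 | no | handed out, not completed | 9 |
| MDS-UPDRS Part 2 | 2.1 to 2.13 | no | handed out, not completed | 9 |

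**Step 1: computable changes.** The planned days are 1, 3, 6, 8, 11, 14, 17, 24 and 28, which is 9. A within-instrument change needs an entry in the last column and in one of the two columns before it. No row has both, so 0 of 9 changes can be computed from either reference. The TV1 scales are done on arrival, before the first dose in this study, so the opening visit is the natural on-drug reference. Visits after a TV4 or TV5 holiday do not schedule the MDS-UPDRS either.

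**Step 2: can the clinic UPDRS stand in as the baseline?**
- Part 1: 4 items against 13 − 7 + 1 = 7 items in Part 1B. The sums are not on the same scale.
- Part 2: 17 − 5 + 1 = 13 items against 13. The counts match, but the instruments and the mode differ. The protocol says of the clinic version that "this will be assessed by a qualified rater", while the home version is self-administered. A difference would confound stopping drug with changing instrument and rater.

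**Step 3: what each possible reference allows.**
- As planned: 0 of 9.
- Day 1 as reference: Days 3 to 28, so 9 − 1 = 8 differences. None is a change from on-drug status, because withdrawal starts when the visit's activities end and Day 1 is already off drug.
- One MDS-UPDRS completion at the opening visit: 9 of 9 changes from LDOT.

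**Step 4: is the departure declared?** SAP Section 11 describes one change from the protocol, the handling of CVT-301-003 and CVT-301-009 patients in the efficacy analyses. It does not mention the dropped change analysis for these scales.

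**The case against.** The strongest reply is that the governing plan can be run. The SAP supersedes the protocol where they differ (Protocol Section 12, SAP Section 2), and SAP 9.16 asks only for actual values, which fits an instrument with no LDOT value. That stands. What remains is an undeclared departure and a summary with little to say, not an analysis that will fail.

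Several stronger readings are tempting, and the documents do not support them:

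- *That the protocol promises an MDS-UPDRS change score.* It names UPDRS Parts 1 and 2. The defect is a mismatch between the instrument named and the one used on those days.
- *That the sub-study cannot answer its question.* The AWQ is the scale assigned to potential withdrawal symptoms (Protocol 11.1.12.6). AWQ, DDS-PC, PHQ-9 and Epworth have on-drug values.
- *That this is the only scale that changes form at home.* The C-SSRS moves from a clinic version to a self-report version (Protocol 11.1.12.2), and SAP 9.9 still plans a shift from LDOT across them.
- *That both clinic parts are rater-scored.* A qualified rater is specified for Part 2 (Protocol 11.2.8); none is named for Part 1 (Protocol 11.3.3).
- *That change from Day 1 repairs the gap.* Any worsening by Day 1 is already in the reference.

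Two further points stand. A new assessment needs a protocol amendment with IRB/IEC approval (Protocol 13.1.2), so this is more than SAP wording. SAP Version 2.0 is dated 29 June 2017, one day before the planned data cut for the second interim, and the documents do not show how many patients had yet to reach the opening visit.

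**Conclusion.** The point holds as an instrument mismatch. No change from an on-drug value, or from TV1, can be computed within one instrument for any of the nine planned days. SAP 9.16 reports raw off-drug values in its place without saying so in SAP Section 11.

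The consequence is limited. One supportive descriptive safety scale loses its reference. The primary spirometry objective and the four withdrawal scales with LDOT values are untouched. It would be wrong to infer from SAP 9.16 as it stands that symptoms on this scale did or did not worsen after stopping.

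The conclusion assumes that the visit lists and time-and-events tables are complete, so that no site collects the MDS-UPDRS in clinic outside them. The gain from the fix depends on how many patients have not yet reached the opening visit, which the documents do not give. This is a cheap improvement, not a threat to the trial's main conclusions.

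**What to change.** 1. **Collect one on-drug value.** Patients who have not yet reached the visit that opens withdrawal (TV4, TV5, TV6 or ET) complete the same self-administered MDS-UPDRS Parts 1B and 2 once at that visit, on arrival in the ON state with the AWQ and DDS-PC and before the in-clinic dose.
2. **SAP 9.16 and its two tables.** Add within-patient change from LDOT to Days 1 to 28 for patients with that value. For patients already past the visit, report within-patient change from Day 1 as an off-drug trajectory, and state that it cannot show change from on-drug status. Label the score Part 1B, as SAP 4.3 already defines it.
3. **Protocol 12.5 and the synopsis.** Name the MDS-UPDRS in both sentences and limit the change analysis to patients with an on-drug value. Changing the name alone would leave an analysis that cannot be done for patients already past the visit.
4. **SAP Section 11.** Declare the departure from the protocol.

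**Cost.** A few minutes per patient for a form already handed out at that visit, a small protocol amendment with ethics approval, and SAP edits, which are allowed until database lock. Treatment is not affected.

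**What it does not buy.** Oral PRN PD medication is permitted during the drug holiday (Protocol 9.4.2), so even a proper change from LDOT would not isolate a withdrawal effect. The report should say so.
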